14.2 Analysis Secondary Endpoints

RNA-seq: Identification of differentially expressed genes at weeks 2, 4, 12 compared to pre-treatment baseline in dupilumab-treated patients within each immune population studied using the statistical program Cuffdiff (paired analysis).

We will also explore whether early molecular changes are predictive of the clinical response to dupilumab at 52 weeks (reduction of EASI and improvement in pruritus score), which could lead to the identification of novel biomarkers.

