	will be performed at screening.
STATISTICS Primary Analysis Plan	CyTOF : One sample paired t test comparing mean change in lesional and non-lesional IL-4 positive, CD4+ T effector cells compared to baseline. RNA-seq : Identification of differentially expressed genes compared to baseline within each immune population studied using the statistical program Cuffdiff (paired analysis).
ETHICAL CONSIDER- ATIONS	This study will be conducted in accordance with applicable laws and regulations and according to the recommendations of International Conference on Harmonization Good Clinical Practice (ICH GCP) guidelines and those of the Declaration of Helsinki (Edinburgh, 2000); only after approval for the study has been obtained from the relevant regulatory authority and relevant independent ethics committee (IEC). The institutional review board (IRB)/IEC must review and approve the protocol and informed consent form (ICF) before any subjects are enrolled. The subject must be consented using the approved ICF before any procedures specified in the protocol are performed.

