CD3, CD19, CD117, CD11b, CD4, CD8a, CD11c, CD14, IL-4, TNFa, CD123, gdTCR, GATA3, IFNg, IL-13, IL-10, IL-4Ra, CD27, IL-33, Tbet, CD152 (CTLA-4), Foxp3, CD33, CD45RO, CD127, IL-25, IL-17A, Ki-67, CD25, RORgt, TSLP, CD38, IL-2, HLA-DR, PD-1, CD56, CD16

RNA-seq cell types for AD

CD4+ T effectors, CD4+ T Regs, CD8+ T effectors

[figure not shown]

Figure 1. Multi-parameter flow cytometric analysis of human skin and atopic dermatitis markers. (A) Example of functional immunoflow cytometry on 4 mm punch biopsy specimen of normal human skin. Tissue was minced and digested for 12 hrs in a digestion cocktail containing collagenase. Cells were washed, stimulated with PMA/ionomycin, and stained for 13-color flow cytometry to detect cell surface proteins and intracellular cytokine production. In contrast to other methods, our protocol does not rely on cell culture or addition of exogenous growth factors such as IL-2, which can substantially alter the phenotype of cells. Foxp3 is a transcription factor that drives the differentiation of regulatory T cells. (B) Gating strategy for atopic dermatitis flow panel. Live CD45+ leukocytes are further subsetted as CD4+ T effector cells, CD4+ T regulatory cells, and CD8+ T effector cells, or innate lymphoid cells type 2 (ILC2). (C) This technique is extremely sensitive, as a biopsy specimen from normal skin (having no appreciable inflammatory infiltrate by routine histology) shows a defined CD4+ and CD8+ T cell population capable of producing specific effector cytokines such as IL-4, IL-17, IFN-gamma, and IL-22.

[figure not shown]

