9.2.5 Skin biopsy procedure

At weeks 0, 2, 4, and 12, four standard 5mm punch biopsies (the approximate size of a pencil-end eraser) will be performed. Of the biopsies performed at each visit, 3 will be from atopic dermatitis lesional skin and 1 will be from non-lesional (clear) skin. After selecting biopsy sites on trunk or extremities (subject preference), the area will be

cleansed with an antiseptic solution and a numbing medication (lidocaine or lidocaine with epinephrine) will be injected to the biopsy area. Each 5mm piece of skin will be removed via punch biopsy and a sterile gauze pad will be placed over the site to control bleeding. The biopsy site may be closed with a stitch. The parents will be provided with post-biopsy care instructions. All standard of care guidelines and sterile technique will be used. These specimens will be analyzed by CyTOF and RNAseq.

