14.4 Sample Size

15 subjects will receive dupilumab for a treatment period of 52 weeks (i.e. last injection on week 50). All subjects will undergo skin biopsies for molecular profiling.

Sample size justification

CyTOF: We estimate the minimum effect size that would be clinically relevant would be a reduction in lesional IL-4 positive, CD4+ T lymphocytes of 10%. The standard deviation of the change in lesional IL-4 positive, CD4+ T lymphocytes in the patient population is estimated at 10%. Therefore, our standardized effect size is 1.00. For the statistical analysis, we will set alpha at 0.05, beta at 0.20 (power = 0.8). The resulting sample size estimate for a one sample paired t test is 9 patients. Our proposal uses a total n=15.

RNA-seq: To determine statistical power to identify differentially expressed genes as measured by RNA-seq, we used the Scotty (Busby et al.) power calculator which uses a t-statistic and incorporates the variance attributable to read depth. Performing RNA-seq on 15 samples before and after treatment to a read depth of 50 million per sample as proposed here, we can detect >97% of transcripts displaying 2X fold change and >80% of transcripts displaying 1.5X fold change with p<0.01 (Figure 4).

[figure not shown]

Fig 4. Power to detect differentially expressed genes using RNA-Seq.

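### The RNA-seq plan asks for a paired analysis from Cuffdiff, a program with no patient term; if it is used, the p-values ignore the pairing and, with positive within-patient correlation, are conservative.

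*Combined protocol and SAP*

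**What the plan says.** Section 14.2 sets the task as "Identification of differentially expressed genes at weeks 2, 4, 12 compared to pre-treatment baseline in dupilumab-treated patients", to be done "within each immune population studied using the statistical program Cuffdiff (paired analysis". The synopsis, in its Statistics row, names the same tool with the same label: "using the statistical program Cuffdiff (paired analysis". Neither place gives a model formula, a patient term, an alternative program, or an account of how the pairing would be carried out.

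The pairing is a real feature of the design. Section 9.2.5 has every patient sampled repeatedly: "At weeks 0, 2, 4, and 12, four standard 5mm punch biopsies", of which "3 will be from atopic dermatitis lesional skin and 1 will be from non-lesional (clear) skin". Section 2.1 lists the sorted populations for sequencing: "CD4+ T effectors, CD4+ T Regs, CD8+ T effectors".

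Section 14.4 supports the RNA-seq part with a Scotty calculation: "Performing RNA-seq on 15 samples before and after treatment to a read depth of 50 million per sample as proposed here", it says, "we can detect >97% of transcripts displaying 2X fold change" and more than 80% of those with a 1.5-fold change, at p<0.01. It describes the calculation as using a t-statistic. It does not say whether that is a one-sample or a two-sample statistic, and it gives no dispersion or within-patient correlation.

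Section 14 promises a detailed SAP before the final analysis, which may modify these methods.

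**The concern.** The plan fixes a program and a property that the program does not have. Cuffdiff takes each condition as a set of replicates and tests between conditions. It has no input for a subject identifier, a block or a covariate. This is general methods knowledge, not something stated in the documents. Given 15 week-0 libraries and 15 week-12 libraries from the same patients, it treats them as 30 independent samples.

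An analyst following the text must therefore drop either the program or the pairing, and the text does not say which. If the program is kept, each test carries between-patient variation that pairing would remove. Section 5.2 defines the secondary endpoint as a count of differentially expressed genes and pathways, so a test that misses true changes lowers the endpoint value itself.

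**Working it through.** **Inputs from the documents.** 15 patients, each sampled before and after treatment; p<0.01; more than 80% detection at 1.5-fold and more than 97% at 2-fold (Section 14.4).

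**Assumptions.** Normal log2 expression with equal SD at both visits, two-sided tests, complete pairs, and a within-patient correlation ρ from 0 to 0.7. The documents give no ρ. The t-tests stand in for the RNA-seq tests and show direction and rough size only.

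**The plan's own figure.** It cannot be reproduced, because Scotty needs dispersion data that the text does not give. As a stand-in, read the 80% at 1.5-fold as the power of a two-sample t-test for one gene:
- Power comes from the noncentral t with 28 df and noncentrality d·√(15/2). Power of 80% at α = 0.01 needs d = 1.327.
- Implied SD = log2(1.5)/1.327 = 0.585/1.327 = 0.44.
- At 2-fold, d = 1/0.44 = 2.27 and power is 99.9%. This does not conflict with the stated figure of more than 97%.

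**Why the unpaired test is conservative.** The true variance of the mean change is 2·SD²·(1−ρ)/15. The unpaired test estimates it as about 2·SD²/15. Its statistic is therefore too small by a factor of about √(1−ρ).

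**Two anchors for power.**
- Anchor A holds the SD at 0.44 and the change at 1.5-fold. The standardised paired change is then 1.327/√(2(1−ρ)): 0.94 at ρ = 0 and 1.33 at ρ = 0.5.
- Anchor B takes a gene that the paired test finds with 80% power at every ρ (standardised paired change 1.003; 14 df). The raw change is 1.003·√(2(1−ρ)) SD, which shrinks from 1.42 SD at ρ = 0 to 0.78 SD at ρ = 0.7.

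Both tests were simulated on the same correlated data, with at least 100,000 data sets per setting:

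| Assumed ρ | True error of unpaired test at nominal 1% | A: unpaired power | A: paired power | B: unpaired power (paired 80%) |
|---|---|---|---|---|
| 0 | 1.0% | 80% | 73% | 86% |
| 0.2 | 0.46% | 82% | 84% | 78% |
| 0.3 | 0.27% | 84% | 89% | 71% |
| 0.5 | 0.06% | 87% | 97% | 51% |
| 0.7 | <0.01% | 90% | >99% | 20% |

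The paired test holds its error at about 1% throughout. Under A, ignoring the pairing costs about 2, 5, 10 and 10 points at ρ = 0.2, 0.3, 0.5 and 0.7, and gains 7 points at ρ = 0. Under B it costs about 2, 9, 29 and 60 points, and gains 6 at ρ = 0.

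**The case against.** The strongest reply has four parts.

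- **The premise is external.** No section describes how Cuffdiff works. That is true, and the point depends on it. It is, however, a basic property of a named program, not a figure recalled from a study.
- **The harm is conditional.** It needs positive within-patient correlation, and fresh biopsies are taken at each visit. At correlations up to about 0.1 the unpaired test is slightly more powerful under either anchor. This stands.
- **The error is on the safe side.** With complete pairs, ignoring the pairing leaves the mean log change as it is and alters only its standard error. A reader might infer that the gene lists would be inflated with false positives. The calculation shows the opposite.
- **The later SAP can correct it.** It can, but nothing in the current text does so or marks the method for change.

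Four stronger readings also go too far. A fall in power from 80% to 20% belongs to Anchor B at ρ = 0.7; under the anchor nearest to the plan's own figure, unpaired power never drops below 80%. It is too much to say that the only internal control is lost: the comparison with baseline remains, and non-lesional skin from the same patients is sampled too. Nor do the documents say that the Cuffdiff gene lists feed the search for predictors of week-52 response; Section 14.2 speaks only of early molecular changes. Finally, the text does not settle which half of the instruction an analyst would abandon, so unpaired p-values follow only if Cuffdiff is kept.

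**Conclusion.** The instruction contradicts itself as written in Section 14.2 and the synopsis: the named program cannot deliver the named analysis. If Cuffdiff is run, the p-values for weeks 2, 4 and 12 against baseline ignore the pairing. With positive correlation the test is then conservative, and genes that truly change are missed. The loss is about 2 to 10 points of power at correlations of 0.2 to 0.7 if the plan's 80% at 1.5-fold is a two-sample figure. It is larger for genes whose detection depends on the pairing. These sizes rest on assumed correlations and a normal analogue.

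The effect is confined to the RNA-seq endpoint, which is secondary even though the synopsis lists its method under the primary analysis plan. The primary CyTOF analysis is a paired t-test and is not touched. This should be fixed before analysis, but it does not threaten the trial's primary result.

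**What to change.** In the synopsis and Section 14.2, replace Cuffdiff with a method that carries a patient term: for example edgeR or DESeq2 with design ~ patient + week, or limma-voom with patient as block. Fit it separately for each cell population and for lesional and non-lesional skin, with weeks 2, 4 and 12 against week 0 as the contrasts. Fitting all four visits together is an option and is not needed to cure the defect. In Section 14.4, either state that the Scotty figures come from a t-statistic calculation and not from the paired model, or recompute them for that model and give the assumed dispersion and correlation. The promised SAP can carry the change if it is settled before the data are analysed.

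Biopsies, libraries and reads stay the same, and the software is free. The costs are a pipeline built on gene counts instead of Cufflinks output, and a small loss of power if within-patient correlation is near zero (80% to 73% under Anchor A, 86% to 80% under Anchor B).

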14.3 Safety Data

Safety and tolerability data will be summarized for the treatment group, which is the 15 subjects who receive treatment with dupilumab.

Adverse event rates will be coded by body system and MedDra classification term. Adverse events will be tabulated and will include the number of patients for whom the event occurred, the rate of occurrence, and the severity and relationship to study drug.

14.4 Sample Size

15 subjects will receive dupilumab for a treatment period of 52 weeks (i.e. last injection on week 50). All subjects will undergo skin biopsies for molecular profiling.

Sample size justification

CyTOF: We estimate the minimum effect size that would be clinically relevant would be a reduction in lesional IL-4 positive, CD4+ T lymphocytes of 10%. The standard deviation of the change in lesional IL-4 positive, CD4+ T lymphocytes in the patient population is estimated at 10%. Therefore, our standardized effect size is 1.00. For the statistical analysis, we will set alpha at 0.05, beta at 0.20 (power = 0.8). The resulting sample size estimate for a one sample paired t test is 9 patients. Our proposal uses a total n=15.

RNA-seq: To determine statistical power to identify differentially expressed genes as measured by RNA-seq, we used the Scotty (Busby et al.) power calculator which uses a t-statistic and incorporates the variance attributable to read depth. Performing RNA-seq on 15 samples before and after treatment to a read depth of 50 million per sample as proposed here, we can detect >97% of transcripts displaying 2X fold change and >80% of transcripts displaying 1.5X fold change with p<0.01 (Figure 4).

[figure not shown]

Fig 4. Power to detect differentially expressed genes using RNA-Seq.

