	
12. Treatment with oral antibiotics within 2 weeks of the baseline visit.
 
13. Treatment with any cell-depleting agents including but not limited to rituximab: within 6 months before the baseline visit, or until lymphocyte count returns to normal, whichever is longer, or use of other biologics: within 5 half-lives (if known) or 16 weeks prior to baseline visit, whichever is longer.
 
14. Physical or laboratory exam not within clinically acceptable limits.
 
15. Subjects possess other diagnoses that, in the investigator's opinion, preclude him/her from safely participating in this study or interfere with the evaluation of the subject's atopic dermatitis.
 
16. At baseline visit, the subject does not have sufficient clear skin for which to perform patch testing as determined by the investigator's opinion, which is also defined as approximately 50-75% of skin on the back clear of atopic dermatitis.
 
17. History of known or suspected intolerance to any of the ingredients of the investigational study product.
 
18. Pregnant or nursing (lactating) women, where pregnancy is defined as the state of a female after conception and until the termination of gestation, confirmed by a positive hCG laboratory test (>10 mIU/mL).
 
19. Women of child-bearing potential, defined as all women physiologically capable of becoming pregnant, unwilling to use effective contraception during the study and for 6 weeks after stopping treatment.
 
For healthy control subjects:
 
 1. No areas of non-inflamed skin. 2. History of autoimmune disease. 3. Subject is younger than 18 years of age.
STUDY TREATMENT	Dupilumab (Dupixent ®) 600 mg SC at week 0, then 300 mg SC every other week.
STUDY DURATION	The total duration of the study is expected to be 104 weeks: 52 weeks for recruitment and 52 weeks for site visits.
PRIMARY ENDPOINT	Percentage change from pre-treatment baseline of CD4+ T effector cells in lesional and non-lesional skin expressing IL4 at weeks 2, 4, 12 in dupilumab-treated patients.
SECONDARY ENDPOINT	Differentially expressed genes and pathways in each cell population at weeks 2, 4, 12 compared to pre-treatment baseline using RNA-seq.
SAFETY EVALUATIONS	Safety and tolerability will be assessed by adverse events, vital signs, physical examinations (including skin examinations and injection-site evaluations), and concomitant medication review. Laboratory assessments

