3 STUDY OBJECTIVES

3.1 Primary Objective

Perform quantitative analysis of the immunologic and genetic changes in immune cell populations in lesional and non-lesional skin after dupilumab treatment (15 AD patients) at weeks 2, 4, 12 compared to baseline week 0. The immunologic and genetic profiles in AD patients will also be compared to healthy control skin surgical discard specimens (n=15). The primary endpoint is the percent change from pre-treatment baseline of CD4+ T effector cells expressing IL-4 at weeks 2, 4, 12 in dupilumab-treated patients.

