5.2 Secondary Analysis Endpoint

Number of differentially expressed genes and pathways in each cell population at weeks 2, 4, 12 compared to pre-treatment baseline using RNA-seq.

We will also explore whether early molecular changes are predictive of the clinical response to dupilumab at 52 weeks (reduction of EASI and improvement in pruritus score), which could lead to the identification of novel biomarkers.

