14 STATISTICAL METHODS AND CONSIDERATIONS

Prior to the analysis of the final study data, a detailed Statistical Analysis Plan (SAP) will be written describing all analyses that will be performed. The SAP will contain any modifications to the analysis plan described below.

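### Does RNA-seq power quoted at p<0.01, with no stated rule for calling genes, need to be corrected?

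*Combined protocol and SAP*

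**What the plan says.** Section 14.4 gives the RNA-seq power for 15 patients sampled before and after treatment, at 50 million reads per sample, from a calculator based on a t-statistic: "we can detect >97% of transcripts displaying 2X fold change and >80% of transcripts displaying 1.5X fold change with p<0.01". No variance is given, and no adjustment for the number of transcripts is mentioned.

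Section 5.2 defines the secondary endpoint as "Number of differentially expressed genes and pathways in each cell population at weeks 2, 4, 12 compared to pre-treatment baseline using RNA-seq". The synopsis words it without the count: "Differentially expressed genes and pathways in each cell population at weeks 2, 4, 12 compared to pre-treatment baseline using RNA-seq". Section 14.2 describes the analysis as done "within each immune population studied using the statistical program Cuffdiff (paired analysis"), and the synopsis says the same. Neither gives a p-value, FDR or fold-change cut-off.

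Section 2.1 lists the sequenced populations as "CD4+ T effectors, CD4+ T Regs, CD8+ T effectors". Section 14 opens by stating that, before the final data are analysed, "a detailed Statistical Analysis Plan (SAP) will be written describing all analyses that will be performed".

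**The concern.** A count of genes has no defined value until the calling rule is fixed, and the only RNA-seq threshold in the documents is the p<0.01 attached to the power statement. Three cell types at three weeks make 9 transcriptome-wide comparisons, or 18 if lesional and non-lesional skin are analysed separately, since Section 3.1 covers both.

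Two things would be at stake. If genes were called at p<0.01, false calls would add straight to the endpoint and could feed the exploratory search for biomarkers of week-52 response. If an FDR rule were used instead, the power quoted in Section 14.4 would belong to a different, possibly more lenient, test than the one applied.

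**Working it through.** **Inputs from the documents.** 15 pairs; power 80% at 1.5-fold and 97% at 2-fold at p<0.01 (stated as lower bounds, taken here as exact); a t-statistic (Section 14.4).

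**Assumed, not in the documents.** Two-sided paired test; Benjamini-Hochberg (BH) at 5% FDR; share of transcripts that truly change, π; 10,000 transcripts; the spread of SDs between transcripts.

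**1. The plan's own figures.** They cannot be derived afresh, because no variance is given and Figure 4 is not shown in the text reviewed. They can be checked for coherence.
- One common SD: 80% power at two-sided 0.01 with 14 degrees of freedom needs a noncentrality of 3.886, so d = 3.886/√15 = 1.00. A 2-fold change multiplies this by 1/log2(1.5) = 1.71 and gives 99.9% power. That is compatible with a bound of more than 97%, but well above it.
- SDs that vary between transcripts: a lognormal SD of the log2 change (median 0.506, log-scale SD 0.411) gives 80% and 97% together.

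The two stated figures are therefore coherent, and nothing in the documents contradicts them.

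**2. If p<0.01 were the calling rule.** False share of called genes = 0.01(1−π) / [0.01(1−π) + 0.80π].
- π = 5%: 0.0095/(0.0095 + 0.040) = 19%
- π = 10%: 0.009/(0.009 + 0.080) = 10%
- π = 20%: 0.008/(0.008 + 0.160) = 4.8%

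**3. If 5% BH were the rule.** The per-transcript threshold a solves a = 0.05 × [(1−π)a + π × power(a)]. Power for 1.5-fold changes, starting from 80%:

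| Share changing | a (common SD) | Power, common SD | Power, SDs varying to match 80% and 97% |
|---|---|---|---|
| 5% | 0.0013 | 48.3% | 62.9-66.3% |
| 10% | 0.0033 | 63.9% | 71.0-72.5% |
| 20% | 0.0080 | 77.1% | 78.3-78.5% |
| 24% | 0.0100 | 80.0% | 80.0% |
| 30% | 0.0129 | 83.2% | not run |

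The ranges in the last column come from lognormal SDs, gamma variances and inverse-gamma variances; the 24% entry was run with lognormal SDs only.

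Break-even: setting a = 0.01 gives 0.20 = 0.01(1−π) + 0.80π, so π = 0.19/0.79 = 24.1%. Above that share, p<0.01 is the stricter of the two rules. With an adaptive FDR method, break-even falls to about 19%.

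**4. How firm is the 48%?** It comes from the common-SD model, which gives 99.9% rather than 97% at 2-fold. It also takes the bound of more than 80% as exactly 80%; starting from 85%, the same model gives 58.5% at π = 5%. If the calculator used a two-sample t-statistic, which Section 14.4 does not settle, the figure is 54.8%.

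**5. Effect on the count.** With 10,000 transcripts, 500 of them changed by 1.5-fold:
- p<0.01: 500 × 0.80 + 9,500 × 0.01 = 400 + 95 = 495 genes.
- 5% BH, common SD: about 242 true + 12 false = 254.
- 5% BH, lognormal SDs: about 323 true + 16 false = 339.

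**The case for a change.** The strongest case for a change does not depend on the power figures. Section 5.2 lists a count as an endpoint, and under the assumptions of step 5 the count moves by a factor of 495/339 = 1.5 to 495/254 = 1.9 with a rule that nobody has fixed. The promise of a SAP is general and is timed to the final data, while the RNA-seq samples are complete by week 12, so a threshold could be chosen with the gene lists in view. A rule set in the SAP would also leave Section 14.4 describing a different test.

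The absence of a stated rule stands, and so does the dependence of the count on it. The rest weakens on inspection. Section 14.4 does not adopt p<0.01 for calling genes, and no section says that a list made that way feeds the biomarker work. The size of any mismatch with the later rule is unknown: it runs from 32 points (80% to 48%) through zero to a gain, according to a share the documents do not give. Section 5.2 sets no hypothesis, target or decision on the count, so it describes a mechanism and does not serve as a test that could be passed by choice of threshold. Adding an FDR rule within each cell population and week would also leave the pathway half of the endpoint, and the multiplicity across 9 or 18 lists, where they are now.

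**Conclusion.** No change to the plan follows. The protocol leaves out a detail that Section 14 assigns to the SAP and that analysts of transcriptome data would be expected to fill with a conventional FDR rule. The stated power is labelled with its threshold, its two figures are coherent, and it is not shown to be wrong.

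The possible overstatement for 1.5-fold changes under a 5% BH rule is about 7-17 points if 5-10% of transcripts change, using models that match both stated powers. It is 1.5-1.7 points at 20% and nil at about 24%. The figure of 48% belongs to the common-SD model, which overshoots the stated 2-fold power. All of this rests on an assumed FDR level, share and variance, and on lower bounds taken as exact.

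The endpoint is secondary and the study is single-arm and mechanistic. The separate CyTOF calculation in Section 14.4 asks for 9 patients, and 15 are planned. Restating the RNA-seq power would not alter that number, the samples taken or any finding.
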